10.4 Rationale for the Exclusion of Cognitively Impaired Subjects

Cognitively impaired and institutionalized persons will not participate in this study. Subjects must be able to provide informed consent, and understand and comply with the supplement plan and follow-up.

10.5 Inclusion of NIH Staff

NIH staff (employees, NIH contractors, special volunteers, guest researchers, and trainees) may voluntarily participate in this protocol.

- If the individual requesting to participate in the protocol is a co-worker, the consent from the NIH staff member (co-worker) will not be obtained by the staff member's direct supervisor but by another research staff member approved for obtaining informed consent who is not a co-worker.
- Recruitment, enrollment and compensation of NIH employee subjects will be consistent with the Guidelines for the Inclusion of Staff in NIH Intramural Research Studies (April 2016) (SOP 14F, Appendix C) and NIH Policy Manual Chapter 2300-630-3 and the Leave Policy for NIH Employees Participating in NIH Medical Research Studies.
- Neither participation nor refusal to participate as a subject in this protocol will have an effect, either beneficial or adverse, on the participant's employment or position at NIH.
- The consenting staff member will make the NIH Information Sheet on Staff Research Participation available to staff members who are considering enrolling in research. (SOP 14F, Appendix C, Appendix A of the protocol)
- Employee subjects' privacy and confidentiality will be respected by protocol and consenting staff the same as for all subjects participating in research protocols. However, all subjects will be made aware that there are limits to these protections.

10.6 Evaluation of Benefits and Risks/Discomforts

Benefits:

There are no direct benefits to the patient. However, omega-3 supplements and omega-9 supplements have been shown to decrease pro-atherogenic lipid levels in several clinical trials. Routine clinical laboratory testing and disclosure of results will be available to all subjects. Subjects are also entitled to being notified of results from the clinical cardio-ankle vascular measurement, if requested.

Risks/Benefit Analysis:

As of May 2, 2019, this study is now closed to new subject accrual and continues in data analysis only and the level of risk is minimal.

Risk (45 CFR 46.102 (h)(i)): The research involves no more than minimal risk to subjects and no prospect of direct benefit to individual subjects, but likely to yield generalizable knowledge about the condition or disorder under study.

Study Agent:

17-H-0050: Effect of Fish Oil Enriched In Omega-11 Fatty Acid On Lipoprotein Metabolism In Adults
PI: [name].
Date: May 2, 2019
Version: 5.0 (Amendment D)

Sardine oil- or LCMUFA-rich fish oil, have minimum risk to subjects.

Generally, adverse effects of fish oil supplements may include atrial fibrillation of new onset and increased propensity for bleeding. Drug interactions may exist between individuals receiving Aspirin or clopidogrel (Plavix).

The most common side effects of fish oil include taste perversion, and eructation (belching). Participants will be notified of these effects in the informed consent document. Any subject exhibiting symptoms such as palpitations, rapid heart rate, or shortness of breath will be instructed to go to the emergency room immediately and be withdrawn from the study. Individuals with an unknown allergy to fish or shellfish not disclosed at screening may experience an anaphylactic reaction, which will also be instructed to go immediately to an emergency room and will require withdrawal from the study. In rare cases, fish oil supplement can trigger allergic reactions. Symptoms may include difficulty breathing, swelling of the face, fever, or flu-like symptoms and a skin rash. Some studies reported consumption of omega-3-fatty acids is associated with a prolongation of bleeding time. However, the prolongation of bleeding time has not been shown to surpass normal limits and did not result in clinically significant bleeding episodes^{33,34}. Any patient currently treated with an anticoagulant will be excluded from this study.

Oleic acid-rich olive oil, commercially available olive oil supplements have minimum risk to subjects.

Blood Draw: Subjects may feel lightheaded or dizzy after having blood drawn. There may be pain at the vein puncture site and a slight risk of bruising. To minimize this risk, the routine blood-drawing protocol will be followed and pressure will be applied to the area.

The protocol will follow the NIH Clinical Center MAS policy M95-9 guidelines for limits of blood drawn for research purpose in the Clinical Center. For adults, no more than 10.5 mL/kg or 550 mL, whichever is smaller, will be drawn for research purposes over any 8-week period.

Cardio-Ankle Vascular Index (CAVI): Inflation of blood pressure cuffs may cause transient discomfort. Subjects with fragile skin may suffer minor trauma (as per ABIs, related to usual BP measurements). This procedure involves the use of a VaSera VS-1500N system; an FDA approved vascular screening system.

EKG: Up to 12 self-adhesive electrodes will be attached to the subject's arms, legs and/or chest. Some skin irritation can occur where the electrodes are placed. Once the electrodes are placed, the test will begin. After the test, the electrodes are removed. The subject may have minor discomfort, similar to removing a bandage, when the electrodes are removed. Rarely, a reaction to the electrode adhesive may cause redness or swelling where the patches were placed.

10.7 Protocol Consent Processes and Documents

Each subject will receive an oral and written explanation of the goals, procedures, and risks of this study. The original, signed informed consent document will be placed in the medical record, and the subject will receive a signed copy of the informed consent document. A copy will also be placed in the shadow chart. A member of the protocol team will be available to answer questions about the study to be performed.

If there is an unexpected enrollment of a research participant for which there is no translated extant IRB approved consent document, the principal investigator and or those authorized to obtain informed consent will use the Short Form and Oral Consent Process as described in MAS Policy M77-2, NIH HRPP SOP 12, 45 CFR 46.117 (b) (2), (If a study with an IND or IDE, also cite 21 CFR50.27 (b) (a)). The summary that will be used is the English version of the extant IRB approved consent document.

We request prospective IRB approval of the use of the short form and oral consent process for up to a maximum of 5 participants in a given language and will report to the IRB at the time of continuing review of the frequency of the use of the Short Form. Should we reach the threshold of 5 we will have that consent document translated into the given inherent language and, we will seek individual IRB approval for any additional short form needs pending the full translation of the IRB approved consent document.

Participation of NIH Staff

If the individual requesting to participate in the protocol is a co-worker, the consent from the NIH staff member (co-worker) will not be obtained by the research coordinator or the employee's direct supervisor but by another research staff member who is approved for obtaining informed consent, and who is also not a coworker.

10.8 Patient Advocate

A patient's rights representative is available to patients on this protocol. The representative can be reached at [contact] and is located in Building 10. Patients may ask any questions about the study and may withdraw their consent at any time.

11. Conflict of Interest

DSP Gokyo Food & Chemical Co., Ltd. Swanson Health Product Inc. and Nippon Suisan Kaisha, Ltd. are providing the supplements for this study to NIH without charge. No NIH investigator involved in this study receives any payment or other benefits from DSP Gokyo Food & Chemical Co., Ltd. Swanson Health Product Inc. or Nippon Suisan Kaisha, Ltd. The principal investigator assures that each associate investigator listed on the protocol title page received a copy of the NIH's Guide to preventing conflict of interest. No members of the research team reported a potential conflict of interest. There are no conflicts of interest with any financial organization regarding the material mentioned in this protocol.

12. Adverse Events, Deviations, and Unanticipated Problem Reporting

12.1 Adverse events (AE)

Definition: Adverse events (AE) are defined by the FDA as any unfavorable or unintended diagnosis, symptom, sign (including abnormal laboratory finding), symptom or disease which either occurs during the study, having been absent at baseline, or if present at baseline, appears to worsen. An unexpected adverse event is one that is not described in the investigator protocol, published literature or the informed consent document.

All AEs, regardless of severity, will be followed until satisfactory resolution. AEs should be reported by the subject up to 30 days following the last dose of study drug.

Adverse events will be attributed (unrelated, unlikely, possibly, probably or definitively) to study medication and/ or disease and AEs will be graded by severity utilizing CTCAE version 4.0. A copy of the criteria can be downloaded at http://ctep.cancer.gov/protocolDevelopment/electronic_applications/ctc.htm.

Reporting: All adverse events occurring during the study, including those observed by or reported to the research team, will be recorded. All adverse events will be reported to the IRB at the time of continuing review.

Exceptions: The following anticipated non-UP adverse events will not be reported to the IRB unless they occur at a rate greater than (greater than 25% of the total n=70) and/or at a severity greater than (i.e. Grade III higher) that known to occur in healthy volunteers:

- Abdominal pain (Grade I & II)
- Diarrhea (Grade I & II)
- Eructation (Grade I & II)
- Taste perversion (Grade I & II)
- Acid-Reflux (Grade I & II)
- Cough (Grade I & II)
- Flatulence (Grade I & II)
- Abdominal discomfort (Grade I & II)
- Constipation (Grade I & II)
- Increased PT/PTT (Grade I & II)

An abnormal laboratory value or changes from an abnormal baseline value will be considered an AE if the laboratory abnormality is characterized by any of the following:

- Results in discontinuation from the study
- Is associated with clinical signs or symptoms
- Requires treatment or any other therapeutic intervention

- Is judged by the Investigator to be of significant clinical impact

If any abnormal laboratory result is considered clinically significant, the investigator will provide details about the action taken with respect to the test drug and about the patient's outcome.

Abnormal laboratory values not associated with clinical symptoms will be evaluated but will not be considered an AE.

The laboratory results will be monitored by healthcare professionals and documented if clinically significant by the MD or any AIs in the study.

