A summary of all SAEs, nonserious AEs, and other events will be recorded and submitted to the Sponsor and FDA in annual progress reports (21 CFR 312.64(b)). Annual progress reports will be submitted within 60 days after the anniversary date of the IND.

Events will be submitted to [name], IND Sponsor at:
[name].
[name]
[name]
[name]

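### Read literally, the closing sentence of section 12.1 takes adverse-event status away from symptom-free laboratory values that three of its own four criteria would count

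*Combined protocol and SAP*

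**What the plan says.** Section 12.1 first gives a general definition of an AE, which counts an abnormal laboratory finding as a kind of sign. It then gives a specific rule for laboratory values: an abnormal value, or a change from an abnormal baseline, is an AE if any one of four conditions holds.

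1. "Results in discontinuation from the study"
2. It is accompanied by clinical signs or symptoms.
3. "Requires treatment or any other therapeutic intervention"
4. "Is judged by the Investigator to be of significant clinical impact"

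For a result considered clinically significant, the investigator must also describe the action taken and the outcome. The laboratory rule closes with: "Abnormal laboratory values not associated with clinical symptoms will be evaluated but will not be considered an AE". A separate line follows: "The laboratory results will be monitored by healthcare professionals and documented if clinically significant by the MD or any AIs in the study".

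AE status has consequences. Events are attributed to the study product or to disease and graded with CTCAE version 4.0. Section 12.1 adds "All AEs, regardless of severity, will be followed until satisfactory resolution" and "All adverse events will be reported to the IRB at the time of continuing review". Under the IND Annual Report heading in section 12.2: "A summary of all SAEs, nonserious AEs, and other events will be recorded and submitted to the Sponsor and FDA in annual progress reports".

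**The concern.** The list and the closing sentence are both operative rules on the same question, and they give opposite answers for one class of value: symptom-free, but leading to withdrawal or treatment, or judged clinically important. Nothing nearby says which prevails. The line on documenting clinically significant results does not say whether those results are AEs.

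The class is a realistic one for this trial. The subjects are healthy adults, and section 10.6 names a greater tendency to bleed as a possible effect of fish oil. Section 6 lists liver enzymes, CK, PT/PTT, blood counts and whole-blood aggregation among the tests. Abnormalities in these can occur without symptoms.

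At stake is consistent AE counting. Two people compiling AEs from the same records could each point to protocol text and report different totals. Someone who follows the closing sentence would show a subject withdrawn for a laboratory value as a withdrawal with no AE attached.

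**Working it through.** No sample size, power or error rate is involved, and the plan states no figure to reproduce. The check is a logical comparison of the two rules, followed by a trace of what depends on AE status.

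**Step 1: compare the rules.** Let C1 to C4 be the four criteria in the order above.

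- List: AE if C1 or C2 or C3 or C4.
- Closing sentence: not an AE if there are no symptoms.

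Reading C2 as symptoms present, there are 2 × 2 × 2 × 2 = 16 combinations.

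- Symptoms present: 8 combinations. The list says AE and the closing sentence is silent, so there is no conflict.
- Symptom-free: 8 combinations of C1, C3 and C4. In 1 none is met, and both rules say not an AE. In the other 8 − 1 = 7 the list says AE and the closing sentence says not.

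So 3 of the 4 criteria cannot operate for a symptom-free value if the closing sentence is taken at its word. These are counts of wording, not of subjects. There is one further mismatch: criterion 2 covers signs or symptoms, while the closing sentence mentions symptoms only, so a value accompanied by a clinical sign but no symptom is also classed both ways.

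**Step 2: trace what a nonserious, symptom-free value that meets C1, C3 or C4 would lose.**

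| Consequence | Section | If not classed as an AE |
|---|---|---|
| CTCAE grading | 12.1 | Lost |
| Attribution | 12.1 | Lost |
| Follow-up to satisfactory resolution | 12.1 | Express duty lost; action and outcome are still described if the value is clinically significant, and laboratory tests recur at each visit (3.2) |
| IRB report at continuing review | 12.1 | Lost as an AE; Grade I–II PT/PTT increases are already exempt below the stated rate |
| Annual sponsor and FDA summary | 12.2 | Not listed as an AE; may still appear as an other event |
| SAE reporting | 12.2 | Unchanged; does not turn on this sentence |
| Unanticipated-problem reporting | 12.4 | Unchanged; does not turn on this sentence |

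**Step 3: look for text that settles it.** The general definition and the appearance of increased PT/PTT among the anticipated AEs both show that a purely laboratory finding can be an AE. They point away from the literal closing sentence, but neither states a precedence.

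**The case against.** The strongest reply is that the closing sentence was never meant as an override. The list is specific and the sentence after it is general, so it reads naturally as the residual case: values that trigger nothing are looked at but not counted. Any other reading leaves three criteria with nothing to do for symptom-free values. This is probably what the authors intended. What remains is that the sentence comes last, is unconditional, and lacks the one word that would make it residual.

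Several stronger readings are tempting, and the documents do not support them.

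- *These values would disappear from reports to the FDA.* The annual summary also covers other events, so such a case can still be reported there. It would not be labelled an AE, and nothing expressly requires that it be included.
- *They would go unrecorded.* Clinically significant results are documented, with action taken and outcome, under either reading.
- *The protocol sends subjects off study for symptom-free laboratory values.* Section 8.1 lists no laboratory threshold for stopping. The liver-enzyme and platelet limits in section 4.2 are entry criteria. Withdrawal for such a value is possible in practice but is not prescribed.
- *The closing sentence alone creates the tension with the general AE definition.* The four-criterion list already narrows that definition, with or without the closing sentence.

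**Conclusion.** The point holds as a wording error in an operative rule, and it is minor. For symptom-free values, the closing sentence contradicts three of the four laboratory criteria. Followed literally, it costs nonserious values that meet those criteria four things: grading, attribution, the express duty of follow-up to resolution, and the IRB's AE report (subject to the existing PT/PTT exemption). In the annual summary it changes how a value is labelled and removes the assurance that it is listed.

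The conclusion assumes only that someone could apply the closing sentence as written. It does not assume that anyone did. The documents give no number of affected subjects. If it is zero, no count changes. A reader might infer that the trial's safety results or its primary comparison are compromised. Neither follows: serious-event and unanticipated-problem reporting stand apart from this sentence, and the total-cholesterol outcome and its test do not use AE status.

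**What to change.** Replace the closing sentence with: *An abnormal laboratory value that meets none of the four criteria above will be evaluated but is not an AE.*

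Section 10.6 says accrual is closed and only data analysis continues, so the counts can still be compiled under one rule. Apply the four-criterion list to existing records:

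- Criteria 1 to 3: use the withdrawal, symptom and treatment records.
- Criterion 4: use only clinical-significance documentation made at the time. Do not ask for new judgements now, because section 3.1 allows each participant's results to be unblinded after both arms.

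State in the report that the list governed.

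The cost is one sentence and a brief check of records already held, with no new samples or visits. One limit is that a value whose importance nobody documented at the time will not be counted under criterion 4. The change also leaves the list narrower than the general AE definition, and does not by itself reconcile the list with Grade I–II PT/PTT increases named as anticipated AEs.

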12.2 Serious Adverse Events (SAE)

Definition: Serious adverse events (SAE) are defined by the FDA as any untoward medical occurrences that result in death, are life-threatening, require or prolong hospitalization, cause persistent or significant disability or incapacity, result in congenital anomalies or birth defects, or are other conditions which in the opinion of the investigator represent significant hazards. All SAEs will be reported to the Sponsor PI, [name].

Reporting: SAEs that do not meet the criteria of Unanticipated Problem (UP) must be reported to the IRB Chair and Clinical Director within 14 days of learning of the event using the NIH problem report form.

Pregnancy itself is not regarded as an SAE unless there is suspicion that the investigational product under study may have interfered with the effectiveness of a contraceptive medication. Any SAEs associated with pregnancy (eg, congenital abnormalities/birth defects/spontaneous miscarriages or any other serious events) must additionally be reported as such using the SAE report form. If pregnancy occurs during the course of this study an unanticipated problem report will be submitted to the Clinical Director and the IRB.

Deaths possibly, probably, or definitely related to the study agent will be reported to the Clinical Director within 7 days after the PI first learns of the event.

Any and all serious adverse events relating to the acquisition of blood samples, such as laceration, dissection, thrombosis of an artery, especially if those events cause injury to the hand requiring surgical correction, will be reported verbally and in writing to the Clinical Director of both the NHLBI and the Clinical Center and the chair of the IRB. The verbal report will occur within 48 hours of the occurrence. The written report of the serious adverse event (e.g., death or life-threatening adverse event) will be reported within 7 days. For all

other serious adverse events relating to the acquisition of blood samples, the written report will be within 15 days.

IND #: Pending

IND Sponsor: [name], NHLBI

The PI will report SAEs to the Sponsor according to the requirements of 21 CFR 312.64(b) and as agreed upon with the sponsor. The Sponsor (or designee) will determine the reportability of the event to the FDA and IND safety report will be submitted to the FDA as required as either an IND Safety Report or Annual report.

IND Annual Report

A summary of all SAEs, nonserious AEs, and other events will be recorded and submitted to the Sponsor and FDA in annual progress reports (21 CFR 312.64(b)). Annual progress reports will be submitted within 60 days after the anniversary date of the IND.

Events will be submitted to [name], IND Sponsor at:
[name].
[name]
[name]
[name]

12.3 Protocol Deviations (PD)

Definition: Protocol Deviations are any change, divergence, or departure from the IRB approved research protocol.

A PD is serious if it meets the definition of a SAE (see section 12.2) or if it compromises the safety, welfare or rights of subjects or others.

Reporting: Serious PDs will be reported to the IRB and Clinical Director as soon as possible but not more than 7 days after the PI first learns of the event. Not serious PDs will be reported to the IRB as soon as possible but not more than 14 days after the PI first learns of the event.

12.4 Unanticipated Problem (UP)

Definition: An UP is any incident, experience, or outcome that meets all of the following criteria:

17-H-0050: Effect of Fish Oil Enriched In Omega-11 Fatty Acid On Lipoprotein Metabolism In Adults
PI: [name].
Date: May 2, 2019
Version: 5.0 (Amendment D)

1. **unexpected** in terms of nature, severity, or frequency in relation to
 - a. the research risks that are described in the IRB-approved research protocol and informed consent document; Investigator's Brochure or other study documents; and
 - b. the characteristics of the subject population being studied; and
2. **related or possibly related** to participation in the research; and
3. places subjects or others at a **greater risk of harm** (including physical, psychological, economic, or social harm) than was previously known or recognized.

Unanticipated Problem that is not an Adverse Event: An unanticipated problem that does not fit the definition of an adverse event, but which may, in the opinion of the investigator, involves risk to the subject, affect others in the research study, or significantly impact the integrity of research data. For example, report occurrences of breaches of confidentiality, accidental destruction of study records, or unaccounted-for study drug. This may be a protocol deviation(s) and/or non-compliance.

Reporting: Serious UPs will be reported to the IRB and Clinical Director as soon as possible but not more than 7 days after the PI first learns of the event. Not serious UPs will be reported to the IRB and Clinical Director as soon as possible but not more than 14 days after the PI first learns of the event.

If pregnancy occurs during the course of this study an unanticipated problem report will be submitted to the Clinical Director and the IRB.

13. Data and Safety Monitoring Plan

Based on clinical trials, the omega-3 fish oil supplements have been well tolerated and are unlikely to increase morbidity and mortality in subjects meeting the inclusion criteria of the study.

Protocol Monitoring

As per ICH-GCP 5.18 and 21 CFR 312.50 clinical protocols are required to be adequately monitored by the study sponsor. The monitoring of this study will be conducted by Clinical Research Associates (CRAs)/Monitors employed by an independent firm and working under an agreement with NHLBI to monitor aspects of the study in accordance with the appropriate regulations and the approved protocol. The objectives of a monitoring visit will be: 1) to verify the existence of signed informed consent form (ICF) and documentation of the ICF process for each monitored subject; 2) to verify the prompt and accurate recording of all monitored data points, and prompt reporting of all SAEs; 3) to compare abstracted information with individual subjects' records and source documents (subject's charts, laboratory analyses and test results, physicians' progress notes, nurses' notes, and any other relevant original subject information); and 4) to help ensure investigators are in compliance with the protocol. The monitors also will inspect the clinical site regulatory files to ensure that regulatory requirements (Office for Human Research Protections-OHRP), FDA and applicable guidelines (ICH-GCP) are being followed. During the monitoring visits, the

17-H-0050: Effect of Fish Oil Enriched In Omega-11 Fatty Acid On Lipoprotein Metabolism In Adults
PI: [name].
Date: May 2, 2019
Version: 5.0 (Amendment D)

investigator (and/or designee) and other study personnel will be available to discuss the study progress and monitoring visit.

The investigator (and/or designee) will make study documents (e.g., consent forms and pertinent hospital or clinical records readily available for inspection by the local IRB, the FDA, the site monitors, and the NHLBI staff for confirmation of the study data

Safety Monitoring

Principal Investigator: Accrual and safety data will be monitored by the PI. The protocol will be continuously evaluated for any unusual or unpredicted complications with the aim of detecting and preventing unacceptable increase in morbidity and mortality over and above that anticipated from niacin.

NHLBI IRB

Accrual and safety data will be monitored and reviewed annually by the Institutional Review Board (IRB). Prior to implementation of this study, the protocol and the proposed patient informed consent document will be reviewed and approved by the properly constituted IRB operating according to the 45 CFR 46 Code of Federal regulations. This committee must approve all amendments to the protocol or informed consent document, and conduct continuing annual review so long as the protocol is open to accrual or follow up of subjects.

FDA: An annual progress report, any amendments to the protocol, and any change in the status of the protocol will be forwarded to the FDA in compliance with 21CFR 312.33

14. Compensation

Compensation will be provided to the subjects for their time and inconvenience of participating on this protocol based on the values listed below:

| Procedures | Inconvenience Unit | \$ | Frequency | Total \$\$ |
|--|--------------------|------|-----------|--------------|
| Outpatient Visit (first hour) | 2 | \$20 | Up to 8 | \$160 |
| Outpatient Visit (additional hours, up to 4 hours) | 1(per hour) | \$10 | Up to 8 | \$320 |
| Physical Examination | 1 | \$10 | Up to 8 | \$80 |
| Screening Blood Draw | 1 | \$10 | Up to 3 | \$30 |
| Research Blood Draw | 1 | \$10 | Up to 6 | \$60 |
| Stool Sample (optional) | 1 | \$10 | Up to 4 | \$40 |
| Diet & Exercise Assessment | 1 | \$10 | Up to 6 | \$60 |
| CAVI | 2 | \$20 | Up to 6 | \$120 |
| EKG (Electrocardiogram), General | 1 | \$10 | Up to 2 | \$20 |
| Total potential compensation: | | | | \$890 |

Subjects will receive full compensation only after completing the entire study. Subjects that fail to complete the study for any reason will not receive compensation.

15. References

